## 1.0 INTRODUCTION

### 1.1 Metastatic or Unresectable Tumors

In 2018, it is estimated that the US cancer prevalence was about 14.5 million Americans, and this is expected to balloon to approximately 19 million Americans by 2024 (American Cancer Society 2019). Metastatic or unresectable disease is the cause of cancer-related morbidity and mortality for about 90% of cancer patients (Chaffer and Weinberg 2011). Clinical presentation of disease can vary widely depending on the site of the tumor, but pain is frequently a presenting symptom (Hamilton et al. 2015).

### 1.2 Radiotherapy for Tumors Needing Palliation

While radiotherapy paradigms evolve, symptomatic palliation is at the forefront of treatment intent (Spencer et al. 2018; Jones and Simone II 2014). As such, appropriate modality, dose, and fractionation continue to be investigated. Ongoing studies suggest hypofractionated approaches are favorable for this population with regimens based on principles of cancer radiobiology, such as the *Spanos Regimen* and the *QUAD SHOT*, having variable success in specific disease sites (Carrascosa et al. 2007; Corry et al. 2005).

Recent data demonstrates that SBRT offers improvements over conventionally fractionated radiotherapy for palliative treatment (Sprave et al. 2018; Nguyen et al. 2019). Three issues limit the utility of SBRT. First, dose escalation can be difficult given the proximity to surrounding OARs (Hartsell et al. 2005; Shiue et al. 2018). Second, it may be unsafe to treat large tumors with SBRT. Retrospective data and secondary analyses from SBRT trials for NSCLC suggest that 5 cm should be the upper limit for which SBRT may be employed (Allibhai et al. 2013; Videtic et al. 2017). Third, SBRT may not be as effective for larger lesions as it is for smaller lesions. Prior studies support this limitation. (Ricco et al. 2017; Masucci 2018)

### 1.3 Spatially Fractionated Radiotherapy (SFRT)

SFRT may address these limitations of traditional SBRT. SFRT relies on beam collimation to create high-dose “peaks,” organized throughout a target volume with intervening low-dose “valleys” (Billena and Khan 2019). SFRT as a 2-dimensional technique is being evaluated in soft tissue sarcoma in a prospective setting (M. Mohiuddin et al. 2009; Mohammed Mohiuddin et al. 2014). In these studies, a single dose of 2-dimensional SFRT was used either alone or in combination with further conventionally fractionated radiation with or without chemotherapy with 1-2 year LC greater than 90% and limited Grade 2-3 skin toxicities.

Lattice radiotherapy is a form of SFRT that uses a 3-dimensional beam arrangement to target high-dose spherical volumes which allows for a more flexible beam arrangement, better normal tissue optimization, and lower exit beam skin dose (X et al. 2010). Classically, SFRT had been planned to achieve a dose fall off to 20-30% of the “peak” dose (Meigooni et al. 2006). Tested approaches for Lattice designate spheres 1-2 cm spaced

2-3 cm apart (center to center) (Amendola et al. 2018; E et al. 2010). Prior studies show that Lattice SFRT can be delivered using IMRT or VMAT (Gholami et al. 2016; Billena and Khan 2019).

#### **1.4 Correlative Studies Background**

In animal models, extreme hypo-fractionation was found to induce infiltration of T-cells (Lugade et al. 2005). Also, SBRT has been shown to alter levels of soluble PD-L1, IFN  $\alpha/\beta/\gamma$ , TNF $\alpha$ , and various interleukins (Trovo et al. 2016; Ellsworth et al. 2017; Walle et al. 2018; Song et al. 2019).

It is hypothesized that SFRT spares interspersed small volumes of normal tissue allowing it to tolerate higher doses of radiotherapy while immune-mediated bystander effects allow for cell kill of areas of tumor receiving a lower dose. This hypothesis is supported by the finding SFRT is associated with increased serum TNF $\alpha$  and that higher levels of TNF $\alpha$  are associated with complete tumor response (Sathishkumar et al. 2002).

SFRT has been shown to elicit a local effect by the “bystander effect” (i.e. effects to tumor cells in the valleys) via secretion of cytokines, induction of cellular repair pathways, and induction of apoptosis (Sathishkumar et al. 2016; Najafi et al. 2014; Asur et al. 2012).

While SBRT and SFRT are both felt to elicit robust immune responses, the immunogenic effects of Lattice SBRT have not been studied.

#### **1.5 Rationale for treatment approach**

Standard palliative radiotherapy regimens may provide limited durability of response in large tumors. Thus, there is a clinical need for a new approach. A standard palliative radiotherapy regimen is 20 Gy in 5 fractions, and therefore it is reasonable to assume that this should be the minimum dose delivered for adequate tumor coverage in an Lattice SBRT plan. Assuming that this represents the 30% isodose (i.e. the “valley”), this would allow appropriate dose escalation in the “peak” to 66.7 Gy (i.e. the 100% isodose). The Lattice SBRT approach may improve symptom response, LC, and better prime the tumor microenvironment for immune response (Ko, Benjamin, and Formenti 2018; Walle et al. 2018; Krombach et al. 2019) compared with canonical palliative radiotherapy doses with the added benefit of less toxicity than a traditional homogenous SBRT plan.

#### **1.6 Study Design**

##### **1.6.1 Overall Design**

This is a study evaluating the safety and efficacy of Lattice SBRT for patients with large tumors ( $\geq 4.5$  cm) planning to undergo palliative radiotherapy. Patients will be enrolled into 1 of 4 cohorts based on their cancer histology (each at least N=10): sarcoma, thoracic cancers (including esophageal), upper abdominal (including hepatobiliary), or pelvic cancers (including gynecologic and lower GI cancers).

Eligible patients will undergo radiotherapy using Lattice SBRT. Lattice SBRT will be prescribed to 20 Gy in 5 fractions delivered every other day with a Lattice SIB to 66.7 Gy in 5 fractions. Patients will be followed for 12 months after the completion of all therapy for efficacy and treatment-related toxicity assessment.

Secondary outcomes will include patient-reported quality of life outcomes. In addition, we will analyze blood-based markers of treatment response, so blood will be drawn prior to and after completion of radiotherapy.

### **1.6.2 Scientific Rationale for Study Design**

Tumor burden incurs significant morbidity in terms of symptomatology, including pain, dyspnea, hemoptysis, and mass effect on surrounding organs. Palliative hypofractionated radiotherapy is known to be a useful modality for control and/or amelioration of such symptoms. However, large tumors are difficult to treat with traditional palliative methods. Hypofractionated radiotherapy may offer insufficient control and SBRT may be associated with a high rate of toxicity.

Dose escalation using SFRT may offer improved local control, symptom relief, and reduced toxicity compared with traditional radiotherapy methods. Also, SFRT has been associated with significant activation of systemic anti-tumor cytokines and chemokines.

Our initial pilot study of SBRT has been successful thus far, demonstrating that Lattice SBRT is safe and effective treatment for large tumors. However, the pilot study has thus far demonstrated significant heterogeneity in the patient population. Patients are enrolled for different indications and tumor types have varied (i.e. treatment of oligoprogressive disease, palliation of pain, palliation of lung cancer for dyspnea, palliation of sarcoma for bleeding). Further, Lattice SBRT has been followed with varied treatments (i.e. medical therapies, surgery), and sometimes no treatment. Given this heterogeneity, objectively determining the effect of Lattice SBRT both on tumor control and patient QoL is difficult.

This trial of Lattice SBRT will attempt to define efficacy and safety using dual primary endpoints for all patients: local tumor control at 6 months and rate of treatment related grade 3+ CTCAE v5.0 toxicity. Secondary endpoints will then evaluate patient reported QoL in 4 pre-specified sub-groups: sarcomas, thoracic malignancies, gastrointestinal malignancies, and pelvic cancers.

### **1.6.3 Justification for Dose**

One standard regimen for palliative radiotherapy is 20 Gy in 5 fractions. In SFRT, the traditional dose gradient between minimum tumor dose and maximum tumor dose is 30% to 100%, respectively. Using 20 Gy in 5 fractions as traditional coverage for lesions needing palliation (i.e. 30% “valley” tumor coverage), the “peak” 100% dose is 66.7 Gy in 5 fractions.

## 1.7 Risk/Benefit Assessment

### 1.7.1 Known Potential Risks

High-dose radiation has been known to cause toxicity to normal tissue. This is manifested variably depending on the area of the body treated. While the potential toxicities can be serious and include death, these toxicities are rare when high-quality, high-dose radiation is delivered within established normal tissue dose constraints using appropriate immobilization, image guidance, and institutional experience.

We have successfully tested Lattice SBRT plans prescribed to 66.7 Gy in 5 fractions using institutional quality assurance protocols similar to conventional SBRT and have implemented this treatment approach in the LITE SABR M1 pilot study with few treatment related toxicities. At the time of this writing, LITE SABR M1 has accrued 15 patients. A review of the first 8 patients and a data safety monitoring report was completed on 4/29/2020. This passed review and found no protocol SAEs. Since that time, we have had one potentially treatment-related grade 3+ toxicity.

Given this experience, we continue to expect that the toxicity risks associated with Lattice SBRT plans to be similar or better than conventional SBRT for large tumors if the required established dose constraints are met. Blood collection prior to and after radiotherapy poses a small risk of pain and bleeding.

## 2.0 OBJECTIVES AND ENDPOINTS

Objectives	Endpoints	Justification for Endpoints
Primary		
To evaluate the efficacy of 5-fraction palliative Lattice SBRT in patients with large lesions who are planning to undergo palliative radiotherapy ( $\geq 4.5$ cm).	Rate of target lesion local control at 6 months per RECIST 1.1	RECIST 1.1 is a standard measure of local control.
To evaluate the acute and sub-acute toxicity of 5-fraction palliative Lattice SBRT in patients with large lesions who are planning to undergo palliative radiotherapy ( $\geq 4.5$ cm).	Rate treatment-related, non-hematologic CTCAE v5.0 Grade $\geq 3$ toxicity at 6 months	SBRT to large tumors is traditionally associated with high dose to OARs, with sequelae of radiation-induced toxicities. As these patients have no effective treatment options, evaluation of the safety of this method of dose-

		escalation with SBRT is warranted. CTCAE v5.0 is a widely accepted standardized measure of treatment-related toxicity.
Secondary		
To assess pain response to Lattice SBRT	For patients that have pain, their pain level will be assessed with the pain Numeric Rating Scale (NRS)	The NRS is an 11-point scale for patient self-reporting of pain. This is selected because it is a reliable and clinically meaningful measure of pain that is extensively used in research and clinical practice.
To assess patient-reported toxicity outcomes	For patients that do not have pain, patient-reported symptom response will be assessed with PRO-CTCAE. A treatment site specific package of PRO-CTCAE measures will be defined for each treatment location (thorax, abdomen, pelvis, extremity)	PRO-CTCAE is a standardized inventory to collected patient reported symptomatic adverse events in clinical trials.
To assess patient reported quality of life outcomes	Patient reported quality of life and functional outcomes will be measured before treatment, after treatment, and at each follow up with the PROMIS Global, Physical Function, Pain Interference, Anxiety, and Depression system	This patient reported outcome inventory was selected because it is a reliable and clinically meaningful measure of patient reported toxicities and functional outcomes.
Exploratory		
To evaluate blood for immune- and tumor damage-associated response with Lattice SBRT	Whole blood will be collected at baseline and after Lattice SBRT for exploratory studies of immune and tumor damage associated-response	The response of immune-related markers will be assessed before and after Lattice SBRT to better understand the immunogenic effects of treatment on tumor.

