## PROTOCOL SUMMARY

Title:	A Trial of Palliative Lattice Stereotactic Body Radiotherapy (SBRT) for Patients with Sarcoma, Thoracic, Abdominal, and Pelvic Cancers
Study Description:	Lattice SBRT will be used to deliver palliative radiotherapy to large ( $\geq 4.5$ cm) tumors for patients with soft tissue sarcomas, thoracic cancers (including esophageal), abdominal, and pelvic cancers. The safety and efficacy of this approach will be assessed.
Objectives:	
Primary Objective:
 
 
1. To evaluate the efficacy and safety of 5-fraction palliative Lattice SBRT in patients with large lesions (<math>\geq 4.5</math> cm) who are planning to undergo palliative radiotherapy. This will be assessed with the co-primary endpoints of target lesion control at 6 months and rate of treatment-related severe toxicity within 6 months.
 
 
Secondary Objectives:
 
 
1. To assess the rate of treatment-related severe toxicity within 12 months of completion of treatment (i.e. late toxicity)
 
2. To assess patient reported toxicity with PRO-CTCAE
 
3. To assess patient-reported QoL with PROMIS
 
4. To assess patient-reported pain
 
 
Exploratory Objectives:
 
 
5. To evaluate blood for immune- and tumor damage-associated response with Lattice SBRT
 

Endpoints:	
Primary:
 
 
1. Rate of local control by RECIST at 6 months
 
2. Proportion of patients with treatment-related grade 3+ CTCAE v5.0 toxicity assessed within 6 months of completion of treatment
 
 
Secondary:
 
 
1. Proportion of patients with treatment-related grade 3+ CTCAE v5.0 toxicity at 12 months.
 
2. PRO-CTCAE assessment at baseline, post-treatment, 30 days, 3 months, 6 months, and 12 months.
 
3. PROMIS physical function, global health, anxiety, and depression assessment at baseline, post-treatment, 30 days, 3 months, 6 months, and 12 months.
 
4. Numeric Pain Scale at baseline, post-treatment, 30 days, 3 months, 6 months, and 12 months.
 
 
Exploratory: Peripheral blood immune-related biomarkers.

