## **5.9 Concomitant Therapy and Supportive Care Guidelines**

Patients may not receive any concurrent systemic therapy with radiation. The interval from last receipt of systemic therapy to the initiation (or re-initiation) of systemic therapy will be at physician discretion. Supportive care will be consistent with standards for palliative radiotherapy, directed by the treating physician.

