As secondary endpoints, this study will evaluate patient reported outcomes through 12 months follow up. Comparisons of patient-reported outcomes such as pain in patients undergoing palliative radiotherapy are notoriously difficult. These can be impacted by the initial indication for palliative radiation (i.e. oligoprogression versus uncontrolled symptom), presence or absence of other tumors outside the target(s), subsequent therapies after treatment, and co-morbidities. This study will attempt to reduce this heterogeneity by studying the secondary endpoints within pre-specified subgroups. Additionally, this study will evaluate PROs using the reliable change index, which allows evaluation of the change of individual patient PROs of comparison to their own baseline.

The RCI utilizes the known retest reliability and standard deviation of a test to calculate the standard error of measurement and standard error of the difference between scores [Jacobson, 1992]. This value represents the level of change associated with statistically significant change from baseline. RCI is calculated as follows:

$$RCI = \frac{x_2 - x_1}{S_{diff}}$$

Where  $x_2 - x_1$  represents an individual's change between timepoints. This can also be reported as a difference in population mean.  $S_{diff}$ , the standard error of the difference between the two scores accounting for reliability of the test, is calculated as:

$$S_{diff} = \sqrt{2(S_E)^2}$$

$$S_E = s_1 \sqrt{1 - r_{xx}}$$

Where  $S_E$  is the standard error of measurement of the test,  $s_1$  is the standard deviation of the test results at the initial time point, and  $r_{xx}$  is the test-retest reliability of the measure. The test-retest reliabilities of PROMIS domains used in this study have been previously evaluated in patients with musculoskeletal conditions and range from 0.85-0.92 [Deyo, 2016].

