The RCI will be calculated for each individual patient for pain score, PRO-CTCAE, and each PROMIS domain between baseline and the 3, 6, and 12 month time points. In order for a change to be deemed statistically reliable at a 90% confidence interval, the Z-score of the RCI must be greater than 1.645. The 90% confidence interval is standard use in the literature when calculating RCI because it increases the sensitivity in detecting reliable change and defines a change which occurs in only 5% of healthy individuals in either direction [Stein, Gray, Schmitt, Hensel]. Changes that exceed this threshold in either direction are likely due to actual change rather than due to chance. Individual changes are reported as either significant increase, significant decrease, or no change.

Mean RCI for each time-point and domain will be calculated to determine significant change on a population level for each sub-group. The  $S_{diff}$  for each domain will be used to calculate a minimum important change at each time-point based on a 90% confidence interval. Lastly, the proportion of individuals in each histology cohort group whose RCI indicated significant increase, significant decrease, or no change in PRO scores will be reported.

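### Pain response to Lattice SBRT is classed from the NRS score alone and analgesic use need not be recorded, so changes in analgesia cannot be separated from changes in pain

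*Combined protocol and SAP*

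**What the plan says.** Section 2.0 states the objective as "To assess pain response to Lattice SBRT" and its endpoint as "For patients that have pain, their pain level will be assessed with the pain Numeric Rating Scale (NRS". The Protocol Summary words the objective more neutrally, as assessing patient-reported pain, and schedules the "Numeric Pain Scale at baseline, post-treatment, 30 days, 3 months, 6 months, and 12 months".

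Section 11.2 gives the analysis: "The RCI will be calculated for each individual patient for pain score, PRO-CTCAE, and each PROMIS domain between baseline and the 3, 6, and 12" months. A change is reliable when "the Z-score of the RCI must be greater than 1.645", applied in either direction. Each patient is then reported as increased, decreased or unchanged. The same RCI values feed a mean for each time point and subgroup, and the proportions in each category for each histology cohort.

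On analgesia, Section 5.9 says only: "Supportive care will be consistent with standards for palliative radiotherapy, directed by the treating physician". The Schedule of Activities and its notes, the pre-radiation evaluation (5.4), the patient-reported outcomes section (5.6), the form list (9.0) and Section 11 do not mention analgesics, opioids or concomitant medication.

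Section 11.2 does warn that "Comparisons of patient-reported outcomes such as pain in patients undergoing palliative radiotherapy are notoriously difficult". It names the indication, tumours outside the target, later therapies and co-morbidities as reasons. Its remedies are subgroups and comparison with the patient's own baseline.

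**The concern.** A pain score is read at whatever level of analgesia the patient is taking that day. If analgesia changes between baseline and follow-up, the change in score mixes the effect of the radiotherapy with the effect of the drugs. The RCI guards against measurement noise only. A fall caused by a higher opioid dose is a genuine fall in pain, so it passes the RCI and is reported under an objective worded as response to treatment. In the other direction, a patient whose pain eased enough to cut analgesics, with the score unchanged, is reported as no change.

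The patient's own baseline does not help, because the confounder is itself a within-patient change. Histology subgroups do not help for the same reason, and there is no control arm to show what analgesic adjustment alone would produce. At stake is whether the pain result of a palliative trial can be interpreted. The co-primary endpoints are not involved.

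**Working it through.** **1. The plan's own cut-off.** The standard normal 95th percentile is 1.6449, and the upper tail beyond 1.645 is 0.0500. The stated limit of 1.645, with 5% in each direction, reproduces.

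**2. Inputs for the limit in NRS points.**
- Formula (Section 11.2): S_E = s1 × sqrt(1 − r) and S_diff = sqrt(2 × S_E²) = s1 × sqrt(2(1 − r)). The limit is 1.645 × S_diff.
- Reliability r: Section 11.2 quotes 0.85 to 0.92 for PROMIS domains in musculoskeletal patients. It gives none for the NRS, so using this range is an assumption.
- Baseline SD s1 of the NRS: not given. Assumed to be 2.0 to 3.0 points.

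**3. Limit, and the chance of being classed as decreased when the only true change is an analgesic-driven fall of d points.** The chance is 1 − Φ((limit − d) / S_diff), using a normal approximation to an 11-point scale.

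| SD | r | S_diff | Limit | d = 0 | d = 2 | d = 3 |
|---|---|---|---|---|---|---|
| 2.0 | 0.92 | 0.800 | 1.32 | 5% | 80% | 98% |
| 2.0 | 0.85 | 1.095 | 1.80 | 5% | 57% | 86% |
| 2.5 | 0.92 | 1.000 | 1.645 | 5% | 64% | 91% |
| 2.5 | 0.85 | 1.369 | 2.25 | 5% | 43% | 71% |
| 3.0 | 0.92 | 1.200 | 1.97 | 5% | 51% | 80% |
| 3.0 | 0.85 | 1.643 | 2.70 | 5% | 33% | 57% |

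Worked example for SD 3.0 and r 0.85: S_diff = 3 × sqrt(0.30) = 1.643, and the limit is 1.645 × 1.643 = 2.70. For d = 2, (2.70 − 2) / 1.643 = 0.43, and the upper tail is 0.33.

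**4. Reading the table.** The limit runs from 1.32 to 2.70 points. An observed 3-point fall exceeds it in all six rows. An observed 2-point fall exceeds it in four rows, but not where the limit is 2.25 or 2.70. Allowing for measurement error, a true analgesic-driven fall of 2 points is classed as a decrease in about 33% to 80% of such patients, and one of 3 points in about 57% to 98%, against a nominal 5%. A lower NRS reliability than the PROMIS range would raise the limit and reduce these chances.

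**5. What the table does not give.** It applies to a patient whose analgesia increased and whose pain fell because of it. The documents do not say how many patients will have pain at baseline, how many will have analgesics raised or lowered, or by how much scores will move as a result. The net effect on the reported proportions therefore cannot be calculated.

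**The case against.** The strongest reply is that the plan claims little here. Pain is a descriptive secondary outcome with no test, success threshold or sample size resting on it. Section 11.2 concedes that such comparisons are difficult, and its mention of later therapies could be read to cover analgesia. This stands as a limit on importance. It does not supply the missing information: acknowledging confounding in general does not let anyone adjust for it.

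Several stronger readings are tempting, and the documents do not support them.

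- **That the plan counts such a patient as a responder.** No responder rule exists. The plan reports a significant decrease, and its remark about actual change versus chance concerns measurement error, not cause. The attribution to Lattice SBRT comes only from the wording of the objective in Section 2.0.
- **That the NRS is the only evidence of palliation.** PROMIS domains, PRO-CTCAE symptoms and local control are also collected. PROMIS Pain Interference and the PRO-CTCAE general pain item are as exposed to analgesia as the NRS, but local control is not.
- **That no case report form captures analgesics.** Section 9.0 lists form names, not fields. What can be said is that the protocol does not require it.
- **That the loss is irrecoverable.** This is a single-institution study, and Section 5.12 allows follow-up by medical records review, so prescriptions could be partly recovered. Actual intake on the day of the score is less recoverable, because questionnaires may be completed by phone or online (5.6).
- **That the share improved is inflated by a calculable number of points.** Any such figure needs inputs the documents lack, and it ignores the opposite bias from reduced analgesia.

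**Conclusion.** The point holds in limited form. Followed exactly, the plan reports an analgesic-driven fall in NRS as a significant decrease under an objective worded as response to Lattice SBRT, and reports a patient who reduces analgesics at a stable score as no change. The documents do not allow the net direction or size of the bias to be determined.

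The only size that can be shown is how easily the limit is crossed: about 1.3 to 2.7 NRS points, resting on an assumed SD of 2 to 3 and on reliabilities borrowed from PROMIS. This is a cheap improvement to a secondary endpoint. It does not affect the co-primary endpoints or the target of 67 enrolled and 47 evaluable patients.

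**What to change.** **Data.** At baseline and each NRS time point, record current analgesic use: opioids as a daily morphine-equivalent dose where available, otherwise a three-way record of increased, unchanged or decreased from baseline. For patients already past baseline, take baseline analgesics from the medical record and flag them as retrospective. The current text is Amendment 9, and accrual status is not stated.

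**Analysis (Section 11.2).** Cross-classify the RCI category by analgesic change, and report:
1. As the pain-response summary, the proportion with a reliable NRS decrease and no analgesic increase.
2. Separately, the proportion with reduced analgesics and no reliable NRS increase, so that the opioid-sparing patient is visible.
3. The NRS-only proportion beside these.

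The full cross-table matters because analgesics may be raised for pain from a tumour outside the target. A patient with both a reliable decrease and an analgesic increase should be read as indeterminate, not as a treatment failure.

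**Cost.** Modest extra data entry at contacts that already take place. A morphine-equivalent dose takes more work than a single tick box, which is why the three-way fallback is offered. The reported response figure may differ from the NRS-only one and may be less favourable. Clinical care is recorded, not altered.

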## **5.0 TREATMENT PLAN**

### **5.1 Study Intervention Description**

Consenting and eligible patients will undergo Lattice SBRT prescribed to a dose of 20 Gy in 5 fractions with a simultaneous integrated boost of 66.7 Gy in 5 fractions. As long as radiotherapy fields do not overlap, treatment of up to 4 other tumor sites are allowed. Lattice SBRT is required for all tumor sites  $\geq 4.5$  cm. Lattice SBRT fractions will be delivered every other day. For sites  $< 4.5$  cm, other planning techniques may be used (i.e. 3D conformal or SBRT). Following radiotherapy, patients will be evaluated for toxicity at 30 days, 3 months, 6 months, and 12 months.

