### **5.4 Pre-Radiation Evaluation**

- History and physical exam by team radiation oncologist
- Assessment of hematologic and metabolic function such as a CBC and renal function panel. This must include assessments of uric acid, potassium, phosphorus, and calcium.
- CT, PET/CT, or MRI of the chest, abdomen, and pelvis
- Completion of baseline NRS pain score (if applicable), PRO-CTCAE, PROMIS Global, Physical Function, Pain Interference, Anxiety, and Depression questionnaires
- Peripheral blood collection.

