### **5.6 Patient-Reported Quality of Life Outcome and Toxicity Measures**

Symptom response and patient-reported quality of life will be measured using the pain numeric rating scale, PRO-CTCAE (abridged as indicated in Appendix D), PROMIS Global, Physical Function, Pain Interference, Anxiety, and Depression questionnaire at the following time points:

1. Within 2 weeks prior to the start of radiotherapy
2. Within 3 weeks after completion of radiotherapy
3. At 30 days after radiotherapy
4. At 90 days after radiotherapy
5. At 180 days after radiotherapy
6. At 360 days after radiotherapy

The patient reported outcomes measures will be conducted using a computer-assisted interview program and may be done in person before/after a routine office visit or over the phone at the preference of the study participant. Patient reported outcomes may also be collected online.

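### The pain-response score is not tied to the Lattice-treated lesion, so pain at other tumours can mask, and less often mimic, the effect that its objective names

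*Combined protocol and SAP*

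**What the plan says.** The objective in Section 2.0 is "To assess pain response to Lattice SBRT". Its endpoint is worded: "For patients that have pain, their pain level will be assessed with the pain Numeric Rating Scale (NRS". The Protocol Summary lists "Numeric Pain Scale at baseline, post-treatment, 30 days, 3 months, 6 months, and 12 months", Section 5.4 asks for "Completion of baseline NRS pain score (if applicable", and Section 5.6 says "Symptom response and patient-reported quality of life will be measured using the pain numeric rating scale". None of these names a lesion or body site, records an index pain site, or gives a rule for pain elsewhere.

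The other pain measures are no closer to the lesion. Appendix D gives every patient a general pain item. It adds regional items for some cohorts, such as abdominal pain for GI cancers, and painful urination and pain with intercourse for pelvic cancers. PROMIS Pain Interference is not lesion-specific.

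On other tumours, Section 5.1 states "treatment of up to 4 other tumor sites are allowed". Lattice is required at every site of 4.5 cm or more; below that size "other planning techniques may be used (i.e. 3D conformal or SBRT". The eligibility criteria (Sections 3.1 and 3.2) do not exclude patients with untreated tumours elsewhere.

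Section 11.2 lists "presence or absence of other tumors outside the target(s" among the things that affect outcomes such as pain. It responds with pre-specified subgroups and the reliable change index (RCI), computed for each patient from baseline to 3, 6 and 12 months.

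**The concern.** The objective asks what a local treatment does to pain. The score, as written, can move or stay still because of pain at a site that the treatment never reached. A patient relieved at the treated lesion but hurting equally elsewhere would be reported as unchanged. A patient relieved only at a small site irradiated by another technique could be reported as having a significant decrease. The trial has a single arm, so no comparator absorbs such changes. The primary efficacy endpoint, by contrast, is tied to the target lesion (Sections 2.0 and 11.2, Appendix E). At stake is whether the reported pain proportions describe the effect of Lattice SBRT or the patient's whole disease and its other treatment.

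**Working it through.** **1. The plan's rule.** Section 11.2 calls a change reliable if the RCI exceeds 1.645, said to occur in 5% in each direction. Check: 1 - Φ(1.645) = 0.0500. This reproduces.

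**2. The limit in NRS points.** From the formulas in Section 11.2, limit = 1.645 × s₁ × √(2(1 - r)). The plan gives no standard deviation (SD) or reliability for the NRS. I assume SD 2.5 and borrow r = 0.85 to 0.92, which the plan states for PROMIS domains only.
- r = 0.85: 1.645 × 2.5 × √0.30 = 2.25, so a fall of 3 whole points is needed.
- r = 0.92: 1.645 × 2.5 × √0.16 = 1.65, so a fall of 2 is needed.
- Over SD 1.5 to 3 the limit runs from 0.99 to 2.70.

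**3. Single cases, taking the reported score as the worse site (assumption).**
- Masking: treated site 7 to 3, another site steady at 6. The score reads 7 to 6. A fall of 1 is no change for any SD of 2 or more (limits 1.32 to 2.70).
- Mimicking: treated site steady at 4, a non-Lattice site 7 to 3. The score reads 7 to 4. A fall of 3 is a significant decrease at every limit in the range.

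**4. Effect on a proportion (all inputs assumed).** Let 60% of patients have a true 4-point fall at the treated site, from a baseline t equally likely to be 4, 5, 6, 7 or 8. A second painful site, if present, stays at o, equally likely to be 2 to 7. That gives 5 × 6 = 30 equally likely pairs. The recorded fall is the smaller of 4 and t - o when t exceeds o, and 0 otherwise.
- Fall of 3 needed: t - o ≥ 3 in 10 of 30 pairs, so one third of true responders with a second site are detected.
- Fall of 2 needed: t - o ≥ 2 in 15 of 30 pairs, so one half are detected.

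Recorded rate = 0.60 × [(1 - q) + q × detected], where q is the share with a second painful site:
- q = 25%: 0.60 × (0.75 + 0.25/3) = 50%; 0.60 × (0.75 + 0.125) = 52.5%.
- q = 50%: 0.60 × (0.50 + 0.50/3) = 40%; 0.60 × (0.50 + 0.25) = 45%.

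**5. The reverse error, same grid.** Hold the treated site steady and let the other site fall by 4 (not below 0). The fall reaches 3 in 1 of 30 pairs and 2 in 3 of 30. Multiplied by q of 25% to 50%, false decreases are about 1% to 5% of patients without relief at the treated site.

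**6. A second model with measurement error.** Treated-site pain has mean 6 and other-site pain mean 5 (each SD 2), half of patients have a painful other site, and the NRS SD and r are as in step 2.
- With 4-point relief at the target only, a reliable decrease is scored in 56% to 71% with the untied score, against 81% to 97% with a lesion-specific one.
- With 4-point relief at the other site only, a false decrease is scored in 9% to 16%, against 3% to 7%. The latter is measurement noise.

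Both models agree in direction, and masking is the larger effect.

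**7. Do the plan's remedies help?** The subgroups (Section 1.6.2) are sarcoma, thoracic, gastrointestinal and pelvic. They do not separate patients by other painful or irradiated sites. The RCI removes stable differences between patients. It does not remove later change at another site, or the limit that another painful site sets on visible improvement.

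**The case against.** Several points on the other side have force.

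- **The plan discloses the problem.** Section 11.2 says such comparisons are difficult and claims only to try to reduce heterogeneity. In palliative care a patient-level pain score is meaningful in itself. That stands as a reason to keep an overall score. It does not make that score a measure of response to Lattice SBRT.
- **The NRS question is not shown.** A reader might infer that patients are certainly asked for overall pain. The documents do not say so; they only fail to tie the score to the lesion. If the form already names the site, a one-line clarification settles the point.
- **Not all pain items are whole-body.** Appendix D has regional items and Section 2.0 promises site-specific PRO-CTCAE packages. These are regional at best and do not cover every cohort.
- **Relief at another irradiated site is not always foreign to the treatment.** Sites of 4.5 cm or more must also receive Lattice, so relief there is a Lattice effect. Mimicking is confined to non-Lattice sites.
- **No responder class exists.** A reader might infer that patients are labelled Lattice responders. Section 11.2 reports only increase, decrease or no change, plus mean RCI, and attaches no decision to pain.
- **The illustration depends on its inputs.** It would be wrong to say that a patient with treated-site pain of 6 and other-site pain of 4 can never register a decrease. The score reads 6 to 4, which misses the limit of 2.25 but passes 1.65. The share with a second painful site has no source in the documents.
- **Timing and scope.** The protocol is at Amendment 9 and planned accrual was 12 to 15 months, so few patients may contribute a new score. Nor does the change address confounding by later therapy. Both are true and limit the benefit.

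**Conclusion.** The concern holds as a gap between a secondary objective and its measure. Pain elsewhere can mask relief at the treated site and, less often, relief at a non-Lattice site can be scored as a significant decrease. The documents do not support saying that this must happen, or how often.

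On the assumed inputs, the recorded proportion falls below a true 60% by about 7 to 10 percentage points if a quarter of patients have a second painful site, and by about 15 to 20 if half do. These figures rest on an assumed NRS SD of 2.5, reliabilities borrowed from PROMIS, an assumed spread of pain scores, other-site pain that stays constant, and a reported score equal to the worse site. The co-primary endpoints and the sample size (47 evaluable, 67 enrolled) are not touched. The change is worth making because it is cheap and makes the endpoint match its objective.

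**What to change.** - In Sections 2.0, 5.4 and 5.6, have the NRS ask for pain at the Lattice-treated lesion(s), taking the worst if there are several, at every time point.
- In Section 11.2, use that score for the pain RCI.
- Keep one overall-pain NRS as a descriptive companion.
- Record and flag patients with other painful sites or sites irradiated by non-Lattice techniques, so that pain results can be shown with and without them.

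The cost is a reworded item and at most one extra question per time point, with no added visits or patients. Patients already assessed without a site-specific score would be reported separately.
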